# **10.** ADVERSE EVENT REPORTING

There is no reason to anticipate any safety concerns arising as a result of any of these diagnostic tests and as such monitoring of adverse events (AEs) to assess the study's safety is not required. Any withdrawals from the study due to intolerability of any of the tests will be regularly reviewed by the Study Management Group (SMG) and the Study Steering Committee (SSC).

# **11. DATA HANDLING AND RECORD KEEPING**

## 11.1. Source data

Source data is defined as all information in original records and certified copies of original records of clinical findings, observations, or other activities in a clinical study necessary for the reconstruction and evaluation of the study. To allow for the accurate reconstruction of the study and clinical management of participants, source data will be accessible and maintained.

Some data variables may be entered directly onto the eCRF, these are clearly identified and detailed in **Table 5**: Source data in mTBI-Predict.

Source data is kept as part of the participants' medical notes generated and maintained at site. In addition, for this study, brain imaging (MRI and MEG) is performed; the source data will be the original output files directly uploaded to the UoB Research Data Store. Similarly, vestibular and physiology workstreams will include the collection of continuously measured electronic data which will be uploaded and stored within the UoB Research Data Store.

Data	Source
Participant Reported Outcomes	The original participant eCRF completed via the app and imported directly into the study database is the source.
Lab results	The original lab report (which may be electronic) is the source and will be kept and maintained in line with normal local practice. For tests performed at NHS labs, information will be transcribed onto the eCRF.
Imaging	The source is the original pseudonymised electronic imaging output file uploaded to the Study Office (via UoB Research Data Store). When data is then interpreted, the eCRF onto which it is transcribed becomes the source.
Mental Health	The MINI Assessment for the DSM-5.
Cerebral Physiology Data	The source is continuously collected raw data files acquired through either Labchart, Spike or native software, uploaded to the Study Office (via UoB Research Data Store). These data include outputs from TCD, , NIRS, EEG, TMS (EMG), Processed and analysed data will be imported into the eCRF in CSV format.
Vestibular Data	
 
Scores will be collected during the following tests:
 
Dix-Hallpike, Walking assessments.
 
Continuous data will be collected and uploaded from the following tests:
 
Posturography, VNG, vHIT, Tympanometry, PTA, VEMPs, EVS.
 

#### Table 5: Source data in mTBI-Predict

Clinical event data	The original clinical annotation is the source document. This may be found on clinical correspondence, or electronic or paper participant records. Clinical events reported by the participant, either in or out of clinic (e.g. phone calls), must be documented in the source documents.
OCT data	The source is the original electronic (CSV format) output file. A copy of this data will be uploaded to the Study Office (via UoB Research Data Store).
Recruitment	The original record of registration is the source. It is held on BCTU servers as part of registration and data entry system.
Withdrawal	Where a participant expresses a wish to withdraw, the conversation must be recorded in the source documents. The outcome of the conversation will also be recorded on an eCRF entered onto the trial database.

# **11.2.** Safety Data

Brain imaging data will remain securely stored at the original imaging centre for the purposes of participant safety. In the event of incidental findings being observed immediately during the assessment, or during processing of the images at UoB, the original imaging centre will refer for radiological review as per local practices.

## **11.3.** Case Report Form completion

An electronic Case Report Form (CRF) system will be used for mTBI-Predict. The CRFs will include (but will NOT be limited to) the following Forms (see

 Table 6: Case report forms in mTBI-Predict).

Form Name	Schedule for submission
Consent and Registration CRF	At the point of registration
Baseline CRFs	At the point of registration
Follow-up CRFs	Following follow-up visit
Participant completed outcome measures	At the time of completion
Brain imaging, cerebral physiology, hormone/steroid biomarker results CRFs	After completion of raw data analysis
Change of status CRF	After the point of reduced participation or death is discovered by the site research team. Also used to collect any other significant change to participant administrative data such as name, contact details,

#### Table 6: Case report forms in mTBI-Predict
gender identity or study withdrawal.

Data should be submitted within two weeks of their submission schedule according to table 6.

In all cases it remains the responsibility of the PI to ensure that the CRF has been completed correctly and that the data are accurate. This will be evidenced by the signature of the PI or delegate. The Site Delegation Log will identify all those personnel with responsibilities for data collection.

The delegated staff completing the CRF should ensure the accuracy, completeness and timeliness of the data reported. This will be evidenced by signing and dating the CRF.

Data reported on each CRF will be consistent with the source data and any discrepancies will be explained. All missing and ambiguous data will be queried. Staff delegated to complete CRFs will be trained to adhere to the mTBI-Predict working instructions.

The following guidance applies to data and partial data:

- Only CRFs provided by the Study Office should be used.
- Time format all times should be in accordance with the 24-hour clock
- Rounding conventions rounding should be to the nearest whole number: If the number you are rounding is followed by 5, 6, 7, 8, or 9, round the number up. **Example**: 3.8 rounded to the nearest whole number is 4. If the number you are rounding is followed by 1, 2, 3 or 4, round the number down. **Example**: 3.4 rounded to the nearest whole number is 3
- Study-specific interpretation of data fields where guidance is needed additional information will be supplied
- Entry requirements for concomitant medications (generic or brand names) generic names should be used where possible
- Missing/incomplete data should be clearly indicated in notes fields all blank fields will be queried by the Study Office
- Protocol and GCP non-compliances should be reported to the Study Office on discovery.

#### **11.4.** Participant reported outcomes

Participant reported outcomes will be completed online via a bespoke app and data periodically imported automatically into the study database. This is a downloaded standalone app which can run on almost all smart phone or tablet devices. It will target assessments to participants via push notifications with text or email (dependent on participant preference) to be used as a backup reminder system if not completed.

#### 11.5. Data management

Processes will be employed to facilitate the accuracy and completeness of the data included in the final report. These processes will be detailed in the study specific Data Management Plan and include the processes of data entry and data queries.

Data entry will be completed by sites via a bespoke Laravel BCTU study database. The data capture system will conduct automatic range checks for specific data values to ensure high levels of data quality. Queries will be raised using data clarification forms (DCFs) via the study database, with the expectation that these queries will be completed by the site within 30 days of receipt. Overdue data

entry and data queries will be requested monthly .

#### **11.6. Self-evident corrections**

No self-evident corrections will be permitted.

#### **11.7.** Data security

#### 11.7.1. BCTU

UoB has policies in place, which are designed to protect the security, accuracy, integrity and confidentiality of Personal Data. The study will be registered with the Data Protection Officer at UoB and will hold data in accordance with the Data Protection Act (2018 and subsequent amendments). The Study Office has arrangements in place for the secure storage and processing of the study data which comply with UoB policies.

The Study Database System incorporates the following security countermeasures:

**Physical security measures:** restricted access to the building, supervised onsite repairs and storages of back-up tapes/disks are stored in a fire-proof safe.

Logical measures for access control and privilege management: including restricted accessibility, access-controlled servers, separate controls of non-identifiable data.

**Network security measures:** including site firewalls, antivirus software and separate secure network protected hosting.

**System management:** the system will be developed by the Programming Team at the Study Office and will be implemented and maintained by the Programming Team.

System design: the system will comprise of a database and a data entry application with firewalls, restricted access, encryption and role-based security controls.

**Operational processes:** the data will be processed and stored within BCTU.

**System audit:** The system will benefit from the following internal/external audit arrangements:

- Internal audit of the system
- Periodic IT risk assessment

Data Protection Registration: UoB's Data Protection Registration number is Z6195856.

#### **11.7.2. BEAR Research Data Store**

Research data for all workstreams needing extensive and/or collaborative analysis (e.g. brain imaging) will be stored on UoB storage (BEAR Research Data Store), accessed via secured network shares mounted on the computers of the relevant workstreams leads and researchers, who have been given specific access to the data. Backups are made overnight from the Research Data Store and any files that are created or changed that day will be backed up. Backups are also copied to a second location for disaster recovery purposes. Access to the data is restricted to those who have been granted access to the project by the Trial Office and they must have a UoB username and password, which can be provided for collaborating researchers. Data can only be accessed off campus through use of the 2-factor authentication remote access service and a log of all activities will be monitored.

#### 11.7.3. Cognitron

H2 Cognitive Designs will design and maintain the study app. The data collected using the app will be processed and stored in a database hosted within Amazon Web Services within the EU-west-2 region

(London). Data within this database are accessible to the research team only, under network and firewall control via 2-factor authentication and encrypted at rest. It will only be connected to participants via trial number; it will collect no other identifiers. H2 Cognitive Designs make daily and weekly backups of this database for assurance and fault recovery. This backup is stored securely under 2-factor authentication within the Amazon Web Services EU-west-1/2 region (Dublin / London). Systems are hardened to at least or exceeding the specifications outlined in NIST-800-700/123 and UK Gov MCSS – Cyber Essentials. Data and information security procedures are developed to the specification required of ISO27001. App data will be imported into the study database and the app will be discontinued; participants will be instructed to delete the app once their follow-up is complete.

### 11.8. Archiving

It is the responsibility of the PI to ensure all essential study documentation and source documents (e.g., signed ICFs, Investigator Site Files, participants' hospital notes) at their site are securely retained for at least 10 years. Archiving will be authorised by BCTU on behalf of UoB following submission of the end of study report. No documents should be destroyed without prior approval from the BCTU Director or their delegate.

The Study Master File will be stored at BCTU for at least 3 years after the end of the study. Longterm offsite data archiving facilities will be considered for storage after this time; data will be stored securely and confidentially for at least 10 years. BCTU has standard processes for both hard copy and computer database legacy archiving.

Once analysis is complete, data which is stored on the BEAR RDS will be archived in the secure UoB BEAR Archive in accordance with UoB Standard Operating Procedures. It will be archived for at least 10 years and will only be accessible upon an application for restoration by an appropriate person such as the Chief Investigator (CI), relevant workstreams lead or Study Office.

# **12. QUALITY CONTROL AND QUALITY ASSURANCE**

### 12.1. Site set-up and initiation

All PIs will be asked to sign the necessary agreements including protocol, clinical trial site agreement and site delegation log, and supply a current signed CV and GCP certificate. All members of the site research team are required to sign the Site delegation log, which details which tasks have been delegated to them by the PI. The Site delegation log should be kept up to date by the PI. It is the PI's responsibility to inform the Study Office of any changes in the site research team.

Prior to commencing recruitment, each recruiting site will undergo a process of site initiation, either face to face or remotely, at which key members of the site research team are required to attend, covering aspects of the study design, protocol procedures, collection and reporting of data and record keeping. Sites will be provided with an Investigator Site File containing essential documentation, instructions, and other documentation required for the conduct of the study.

### 12.2. Monitoring

The central and on-site monitoring requirements for this study have been developed in conjunction with the study specific risk assessment and are documented in the study specific monitoring plan.

### **12.3.** On-site monitoring

For this study, all sites will be monitored in accordance with the study risk assessment and monitoring plan. Any monitoring activities will be reported to the Study Office and any issues noted will be followed up to resolution. Additional on-site monitoring visits may be triggered. PIs and site research teams will allow the mTBI-Predict study staff access to source documents as requested. The monitoring will be conducted by BCTU/UoB staff.

### 12.4. Central monitoring

The Study Office will check received ICFs and CRFs for compliance with the protocol, data consistency, missing data and timing at a frequency and intensity determined by the Data Management Plan. Sites will be sent DCFs requesting missing data or clarification of inconsistencies or discrepancies.

### **12.5.** Audit and inspection

The Investigator will permit study-related monitoring, audits, ethical review, and regulatory inspection(s) at their site and provide direct access to source data/documents. The investigator will comply with these visits and any required follow-up. Sites are also requested to notify the Study Office of any relevant inspections or local audits.

### **12.6.** Notification of Serious Breaches

The sponsor is responsible for notifying the REC of any serious breach of the conditions and principles of GCP in connection with that study or of the protocol relating to that study. Sites are therefore requested to notify the Study Office of any suspected study-related serious breach of GCP and/or the study protocol as soon as they become aware of them. Where the Study Office is investigating whether or not a serious breach has occurred, sites must co-operate with the Study Office in providing sufficient information to report the breach to the REC where required and in undertaking any corrective and/or preventive action.

Sites may be suspended from further recruitment in the event of serious and persistent noncompliance with the protocol and/or GCP, and/or poor recruitment.

# **13. END OF STUDY DEFINITION**

The end of study will be 90 days after the date of the last data capture including resolution of biomarker analyses and data clarifications. This will allow sufficient time for the completion of protocol procedures, data collection and input, and data cleaning. The Study Office will notify the REC and the Sponsor within 90 days of the end of study. Where the study has terminated early, the Study Office will notify the REC within 15 days of the end of study. The Study Office will provide the REC and the Sponsor with a summary of the clinical study report within 12 months of the end of study.

# **14. STATISTICAL CONSIDERATIONS**

### 14.1. Biological variability studies

We will recruit 20 healthy controls and 20 mTBI patients to both the clinical and imaging

assessments days of the study at the 21-day visit (in total 40 healthy controls and 40 mTBI patients). Each participant will then undergo an additional three (or five in the case of imaging for healthy controls) measurements of each biomarker over a 12-day (or 19-day for imaging) period. For some biomarkers (e.g. fluid biomarkers) variability will be assessed by analysis of samples in quadruplicate.

For each of the biomarkers under investigation (see Appendix 1), we will estimate the variability at the within-individual and the between-individual level. For example, for the 20 healthy controls or mTBI patients, if the analytical standard deviation was 0.5, the within-individual standard deviation was 1.0 and the between-individual standard deviation was 2.3, approximate confidence intervals for these estimates would be (0.45, 0.56), (0.79, 1.19) and (1.56, 3.05), respectively. These values would yield an ICC of approximately 80% with a 95% confidence interval ranging from 65% to 89%. All confidence interval estimates have been calculated using simulation. We will not reassess at the 3-month time point as we will assume that variability at 21 days will be greater than at 3 months.

We will use multilevel models to estimate the variability at each level, with log transformation of the biomarker outcomes if necessary, for the healthy and mTBI patients combined and separately. We will express the results from this stage of the study as standard deviations, coefficients of variation, ICCs, reference change values and other relevant variability estimates along with 95% confidence intervals as appropriate. Within the imaging variability study, we will also investigate the variability between centres (University of Birmingham, Aston University, and University of Nottingham) using the same method. For this purpose, the 20 healthy participants will have three additional measurements at the centre used at their 21-day visit, alongside additional imaging visits at the two alternative imaging centres (five total variability visits).

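### Section 14.1: the example intervals for the between-person SD, the within-person SD and the ICC sit too low as 95% confidence intervals for the stated estimates

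*Protocol*

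**What the plan says.** Protocol section 14.1 sets the nested variability study at 20 people per group and assessment type: "We will recruit 20 healthy controls and 20 mTBI patients to both the clinical and imaging" assessment days. On repeats: "Each participant will then undergo an additional three (or five in the case of imaging for healthy controls) measurements of each biomarker". A clinical marker is therefore measured at 1 + 3 = 4 visits.

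The precision is shown by a worked example: "if the analytical standard deviation was 0.5, the within-individual standard deviation was 1.0" and "the between-individual standard deviation was 2.3". For these values, "approximate confidence intervals for these estimates would be (0.45, 0.56), (0.79, 1.19) and (1.56, 3.05), respectively". An ICC of about 80% follows, with a 95% interval of 65% to 89%. The method is given in one sentence: "All confidence interval estimates have been calculated using simulation". The section does not say how the simulations were turned into intervals or how many assay replicates the example assumes. The only replicate number in the section is for some markers: "variability will be assessed by analysis of samples in quadruplicate".

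**The concern.** The between-person interval is centred on (1.56 + 3.05)/2 = 2.305, almost exactly the estimate of 2.3, with arms of 0.74 below and 0.75 above. A confidence interval for an SD that rests on 20 people (19 degrees of freedom) is not symmetric. Its upper arm must be clearly longer, because a small sample can easily give an SD well below the true one. Near-symmetry is what one sees when the true SD is fixed and the estimates are allowed to vary, which answers a different question.

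This example is the only precision argument in section 14.1 for 20 people per group. Section 1.13 says that markers with excess variability may be dropped, and section 14.3 gives the variability results to the Delphi panel. A reader should therefore be able to see how far above its estimate a true SD might lie. The printed upper limits understate that.

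**Working it through.** **Inputs (all from section 14.1).** n = 20 people, k = 4 visits, analytical SD 0.5 (variance 0.25), within-person SD 1.0 (variance 1.00), between-person SD 2.3 (variance 5.29). The number of replicates r is not stated, so 2, 3 and 4 were tried in simulation. The closed forms for the between-person SD and the ICC use one assay per visit.

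**1. Reproducing the printed figures.** Fix the true SDs, simulate the design 400,000 times (triplicate shown) and take the 2.5th and 97.5th percentiles of the estimates:

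| Quantity | Printed | Spread of estimates | Wald on SD scale |
|---|---|---|---|
| Analytical SD | 0.45–0.56 | 0.445–0.555 | 0.445–0.555 |
| Within-person SD | 0.79–1.19 | 0.805–1.192 | 0.806–1.194 |
| Between-person SD | 1.56–3.05 | 1.528–3.060 | 1.531–3.069 |
| ICC | 65–89% | 64–89% | not computed |

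Agreement is within about 0.03. Three or six visits fit the within-person interval worse (spreads of 0.761–1.234 and 0.849–1.149 in triplicate), so the example appears to use four.

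**2. Between-person SD, limits given an estimate of 2.3.** Between-person mean square = 4 × 5.29 + 1.25 = 22.41 on 19 df. Within-person mean square = 1.00 + 0.25 = 1.25 on 60 df. The chi-square quantiles on 19 df are 8.907 and 32.852.
- Lower: √[(19 × 22.41/32.852 − 1.25)/4] = √(11.711/4) = 1.71
- Upper: √[(19 × 22.41/8.907 − 1.25)/4] = √(46.557/4) = 3.41

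The three-level simulation, which allows for error in both mean squares, gives 1.71 to 3.40 or 3.41 for two to four replicates, so the result does not depend on r. The arms are 0.59 below and 1.11 above.

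**3. Within-person SD, limits given an estimate of 1.0.** The mean square of the visit means is 1 + 0.25/r on 60 df, with chi-square quantiles 40.482 and 83.298. The assay part, 0.25/r, is then removed.
- Triplicate: √(60 × 1.0833/83.298 − 0.0833) = 0.83 and √(60 × 1.0833/40.482 − 0.0833) = 1.23
- Quadruplicate: √(60 × 1.0625/83.298 − 0.0625) = 0.84 and √(60 × 1.0625/40.482 − 0.0625) = 1.23

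**4. ICC.** Point value 5.29/(5.29 + 1.25) = 0.81, which reproduces the stated value of about 80%. F = 22.41/1.25 = 17.93. The F quantiles on 19 and 60 df are 0.4406 and 1.9636. Each limit is (F/q − 1)/(F/q + 3):
- Lower: (9.130 − 1)/(9.130 + 3) = 0.67
- Upper: (40.69 − 1)/(40.69 + 3) = 0.91

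The three-level simulation gives 0.68 to 0.91.

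**5. Analytical SD.** Triplicate gives 20 × 4 × 2 = 160 df and limits of 0.451 to 0.561, which round to the printed interval. Quadruplicate gives 20 × 4 × 3 = 240 df and 0.459 to 0.549.

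**6. Size of the shortfall.** The between-person upper limit is 3.41 − 3.05 = 0.36 too low (0.36/3.41 = 11%). The printed width is 1.49 against 1.70, about 12% too narrow. An interval from 1.56/2.3 to 3.05/2.3 times the estimate covers the true between-person SD about 91.4% of the time; the truth lies above it in about 8.3% of samples and below it in 0.3%. If the percentile spread is instead recomputed at each estimate, coverage is 92.8%, with 6.9% of intervals wholly below the truth. A chi-square-type interval covers 95.1%, with misses balanced.

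**The case against.** The protocol calls the intervals approximate. Its wording can also be read as assuming true SDs, in which case the range of estimates to expect is a fair design-stage display. A parametric-bootstrap percentile interval would equal that spread, so the label is loose rather than plainly false. The route is also inferred: a Wald interval fits about as well. All of this stands, but both candidate routes share the downward fault, so the correction does not depend on which was used. The label also matters, because the ICC range is expressly called a 95% confidence interval.

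A reader might infer that the analytical interval is wrong as well, because it does not fit quadruplicate assay. The document does not support that. Quadruplicate is stated for some markers only ("For some biomarkers (e.g. fluid biomarkers) variability will be assessed by analysis of samples in quadruplicate"), the example is generic, and the printed figures are right for triplicate.

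A reader might also infer that the final results will be reported with faulty intervals. That is not supported either. The sentence on simulation describes the planning example. The results are to come from multilevel models, and the interval method may properly be left to the statistical analysis plan.

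**Conclusion.** The point holds for three of the four printed intervals. Read as 95% confidence intervals for the stated estimates, the between-person, within-person and ICC intervals all sit too low. The between-person SD is affected most, with an upper limit about 0.36 (11%) short and coverage near 91%. This rests on normal, balanced data, 20 people and four visits; the between-person result is the same for two, three or four replicates.

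The practical weight is modest. It is tempting to conclude that 20 per group is too few, but section 14.1 sets no precision target, so the corrected figures cannot show that. Nor does the ICC look worse: its proper interval lies slightly higher than the printed one and is no wider. What changes is how large a true SD could be given its estimate.

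**What to change.** In section 14.1, do one of the following:
- replace the three intervals with about 1.71 to 3.41 (between persons), 0.83 to 1.23 with triplicate or 0.84 to 1.23 with quadruplicate (within persons), and 67–68% to 91% (ICC); or
- keep the printed figures and call them the expected range of the estimates when the true SDs are 0.5, 1.0 and 2.3.

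In either case, state the number of assay replicates assumed and how the intervals were obtained. If triplicate is meant, the analytical interval can stay; with quadruplicate, its confidence interval would be about 0.46 to 0.55.

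The cost is one corrected sentence. No visit, sample or participant number changes; only the stated precision of the between-person SD becomes slightly less favourable.

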# 1.13. Rationale for candidate biological variability study (nested study1)

The vestibular, visual, brain imaging, fluid biomarkers and cerebral physiology workstreams will all be involved in the variability study. This is due to the need to estimate the reliability of the techniques used and allow for this in subsequent use of measurements and interpretation of results. Many measures have not been validated. We will validate the techniques used to establish the variation between participants and the variation within participants. It is important for biomarkers to be reproducible. This will inform the main study, as biomarkers that are not fit for purpose due to excess variability may be dropped from further analyses, as we would suggest the need for refinement of these measurements.

Headache, mental health and the cognition workstreams are not included in the variability study. Headache is assessed utilising clinical history to assign phenotype, diaries to describe a patient's experience of their symptoms and patient reported outcome measures (such as the Headache Impact Test-6, or HIT-6) to describe disability. These are already validated tools (HIT-6) and hence variability does not need assessing [211]. The questionnaires involved in the mental health workstream have also been validated [212-218]. Cognitive outcomes will not be looked at due to test-retest reliability having already been determined by the Department of Brain Sciences at Imperial College London (unpublished data) for the cognitive tests proposed.

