## **3.2. Study setting**

- Multi-centre recruitment and clinical assessment through the UK mTBI research network (including Defence Medical Rehabilitation Centre Stanford Hall, University Hospitals Birmingham and further centres)
- Imaging at Centre for Human Brain Health, University of Birmingham; Sir Peter Mansfield Imaging Centre, University of Nottingham; Aston Institute for Health and Neurodevelopment, and Defence Medical Rehabilitation Centre Stanford Hall

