## 9.2. Biological variability study outcomes

The primary outcome is the variability of candidate biomarkers for each workstream.

The secondary outcome is the variability of candidate brain imaging biomarkers between imaging centres (University of Birmingham, Aston University and University of Nottingham). For reasons of capacity as well as real world applicability, scanning in the main study will be split across the different imaging centres.

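### Between-centre imaging variability is to be summarised as a variance from three centres; fixed centre differences from the same scans would be far more informative, and visit day should be in the models

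*Protocol*

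**What the plan says.** Section 9.2 makes centre comparability an outcome in its own right: "The secondary outcome is the variability of candidate brain imaging biomarkers between imaging centres". The reason given is that "scanning in the main study will be split across the different imaging centres".

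Section 14.1 sets the general method, "We will use multilevel models to estimate the variability at each level, with log transformation of the biomarker outcomes if necessary", for patients and controls together and apart, with results given as SDs, ICCs, reference change values and similar measures. For imaging it adds that "we will also investigate the variability between centres (University of Birmingham, Aston University, and University of Nottingham) using the same method". The data for this come from healthy controls only: "the 20 healthy participants will have three additional measurements at the centre used at their 21-day visit", plus one visit to each of the other two centres. With the first scan, that is six scans per person.

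The mTBI patients (20 for the clinical day, 20 others for the imaging day) are measured four times within 12 days, from the 21-day visit (section 7.1). Section 2.2 wants the results to separate real change from random fluctuation, and section 1.13 says that "biomarkers that are not fit for purpose due to excess variability may be dropped from further analyses".

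Section 14.1 gives expected precision for the analytical, within-person and between-person SDs and for the ICC, but none for the centre comparison. It does not say whether time, visit or group enters the models.

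**The concern.** A variance component is only as well estimated as its number of units allows. Twenty people support a between-person SD tolerably well; three centres hardly support a centre SD. Scanning more people does not help, because the number of centres stays at three. The variability study's only secondary outcome would then be reported as a figure with almost no upper bound, often estimated as zero, although the scans can answer the practical question of how far the three centres differ.

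The second issue concerns the patients. Section 1.10.1 cites recovery over 30 days or more for some physiological markers, so a patient measured from about day 21 for 12 days may still be changing. If the model has variance levels only, a common trend counts as within-person noise. That raises the SD and the reference change value and lowers the ICC for markers that follow recovery, and these results feed the decision to drop markers and the Delphi exercise in section 14.3.

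**Working it through.** **Inputs.** From section 14.1: analytical SD 0.5, within-person SD 1.0, between-person SD 2.3; 20 controls with 4 + 1 + 1 scans. From section 7.1: four patient visits within 12 days. Assumed, because the protocol does not give them: home centres split 7/7/6, no person-by-centre variation in the SE below, patient visits at days 0, 4, 8 and 12, and the size of any drift.

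**1. The protocol's own figures.** ICC = 2.3² / (2.3² + 1.0² + 0.5²) = 5.29/6.54 = 0.81, against a stated figure of about 80%. Simulating 20 people × 4 visits × 3 replicates gives intervals of 0.445 to 0.555, 0.81 to 1.19 and 1.53 to 3.05, and an ICC interval of 0.64 to 0.89. The stated ones are 0.45 to 0.56, 0.79 to 1.19, 1.56 to 3.05, and 65% to 89%. They reproduce.

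**2. Centre as a variance component.** With k = 3 centres there are 2 df. The 95% limits for the SD are the estimate times √(2/χ²), where the 2-df chi-square quantiles are −2 ln 0.025 = 7.378 and −2 ln 0.975 = 0.0506.
- Lower: √(2/7.378) = 0.52
- Upper: √(2/0.0506) = 6.3

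This treats the centre means as known without error. With ten centres the factors would be 0.69 and 1.83. Simulating the actual 20 × (4 + 1 + 1) layout:

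| True centre SD | Central 95% of estimates | Estimated as exactly zero |
|---|---|---|
| 0.25 | 0 to 0.59 | 33% |
| 0.5 | 0 to 1.00 | 15% |
| 1.0 | 0 to 1.92 | 4% |

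**3. Centre as a fixed effect, same scans.** The single-scan residual SD is √(1.0² + 0.5²) = 1.118. Each person contributes information 4/6 to each contrast between home and another centre, and 1/6 to the contrast between the two other centres. With home centres in equal thirds, each pair of centres collects (20/3) × (4 + 4 + 1)/6 = 10. The variance of a pairwise difference is then 2/(3 × 10) × 1.25 = 0.0833, so SE = 0.289. The 7/7/6 split gives 0.286 to 0.290. Residual df are 120 scans − 20 people − 2 centre terms = 98, so the 95% half-width is about 1.98 × 0.289 = 0.57.

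Person-by-centre variance can also be estimated. The home replicates give 20 × 3 = 60 df for scan-to-scan error, and the remaining 98 − 60 = 38 df carry the person-by-centre variation. If that variation is present, the SE is larger than 0.29.

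**4. Unmodelled drift in patients.** For a common linear change of D within-person SDs over 12 days, the expected within-person variance is 1 + (D/12)² × Var(t). Here Var(t) = (36 + 4 + 4 + 36)/3 = 26.67.

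| D (assumed) | SD, patients only | ICC | Reference change value |
|---|---|---|---|
| 0 | 1.00 | 0.81 | 3.10 |
| 0.5 | 1.02 | 0.80 | 3.16 |
| 1 | 1.09 | 0.79 | 3.32 |
| 2 | 1.32 | 0.73 | 3.91 |

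The reference change value is 1.96 × √2 × √(within² + 0.5²). In the combined clinical fit, where both groups have four visits, about half the added variance remains: D = 1 gives √((1 + 1.185)/2) = 1.05 and D = 2 gives √((1 + 1.741)/2) = 1.17.

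A fixed visit effect returns 1.00 for a common drift of 1 SD. If drift also varies between people with SD 0.5, it returns 1.02, against 1.11 without the term. It does not remove drift that is purely individual: with mean zero and SD 1, the result is 1.09 either way.

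**The case against.** The strongest reply is that section 14.1 names a class of model and leaves its terms to an SAP. A multilevel model can carry centre, day and group as fixed effects, or centre within person (20 × 3 = 60 units), and the phrase about the same method excludes none of these. For time and group this stands: the protocol neither includes nor rules them out, so that part is a safeguard to write in and not an error found. For centre it stands only in part. The method referred to is one that estimates a variance at each level and the outcome is named as variability, so a centre variance is the natural reading.

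Two stronger conclusions might be inferred, and the documents support neither.
- *The between-centre question cannot be answered.* It can: every control visits all three centres, and step 3 shows usable precision. The weakness is in the summary, not in the data.
- *The within-person SD is biased upward.* That needs both drift and a model without time. Drift of up to 1 SD inflates the SD by at most 9%, inside the protocol's own interval of 0.79 to 1.19. Healthy-only estimates are free of recovery drift, are reported separately and would show a discrepancy. Markers may be dropped, but no cut-off is set and a Delphi panel decides.

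A reader might also want centre in the prognostic models of section 14.4. With three centres that takes 2 of the 10 candidate parameters allowed for headache, depression and PTSD, and it ties predictions to named scanners. It is a trade-off and not a correction. Likewise, "Aston Institute for Health and Neurodevelopment, and Defence Medical Rehabilitation Centre Stanford Hall" in the imaging list of section 3.2 adds a site beyond the three compared, but that does not make the section 14.1 model wrong.

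**Conclusion.** The centre point holds on the natural reading of section 14.1. A centre SD on 2 df has a 95% CI of about 0.52 to 6.3 times its estimate, whereas fixed pairwise differences from the same 120 scans have SE about 0.29, or about a quarter of the single-scan SD of 1.12. This rests on the protocol's example SDs, a near-even split of home centres, and no person-by-centre variation. Fixed effects also suit the purpose, since section 9.2 wants to know about the named centres that share the main-study scanning.

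The drift point is conditional. Its direction is certain if a common trend exists and time is left out; its size is unknown. It is negligible at half a within-person SD over 12 days and material at two (1.32 instead of 1.00). It affects the patient and combined estimates, not the healthy-only estimates or the centre comparison.

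**What to change.** In section 14.1:
1. Fit imaging centre as a fixed effect in the healthy-control imaging model. Report the three pairwise differences with 95% CIs and a person-by-centre variance, and state the expected precision as is done for the other quantities. Say that the results apply to the three named centres.
2. Include day of visit as a fixed effect in the variability models, and patient/control group in the combined fit, before computing SDs, ICCs and reference change values. Without the group term, a mean difference between patients and controls would enter the between-person SD and raise the ICC.

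No extra visit or scan is needed. The cost is a few degrees of freedom. The centre results would not carry over to imaging sites added later, but a centre SD on 2 df would not support that step either.
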